An open-label study to evaluate the pharmacokinetics (PK) of Darunavir (DRV) and Cobicistat (COBI) after a single-oral administration of Darunavir/Cobicistat Fixed-Dose Combination Tablet in Healthy Japanese Adult Subjects

DRV inhibits dimerization of human immunodeficiency virus Type 1 (HIV-1) protease and its enzymatic activity. DRV selectively inhibits cleavage of Gag-Pol polyprotein coded by HIV-1 in the infected cells and thereby suppresses the formation of matured infective viruses. DRV has been shown to have a high affinity to the HIV-1 protease with a K_d of 4.5×10^{-12} mol/L and is less likely to be affected by mutations associated with resistance to HIV protease inhibitors.

COBI selectively inhibits CYP3A. COBI is used as a pharmacokinetic enhancer (booster) for drugs which CYP3A-mediated metabolism could reduce bioavailability and shorten elimination half-life. COBI is used in combination with such type drugs to increase the exposure of the drug.

TMC114 + JNJ-48763364-AAA (Prezcobix®) is a combined formulation of two compounds, DRV and COBI, and is intended for treating patients naive to anti-HIV drug treatment and patients without DRV-resistant mutants previously treated with an anti-HIV drug. Normally, one fixed-dose combination tablet is orally administered to adult patients once daily and must be used in combination with other types of anti-HIV drugs.

This study will be conducted as a postmarketing study to evaluate the pharmacokinetics of DRV/COBI after a single oral administration of Prezcobix to healthy Japanese adult subjects.

OBJECTIVES AND HYPOTHESIS

Objectives

Primary Objective

The primary objective is to evaluate the PK of DRV and COBI after a single oral administration of Prezcobix to healthy Japanese adult subjects.

Secondary Objective

The secondary objective is to evaluate the safety after a single oral administration of Prezcobix to healthy Japanese adult subjects

Hypothesis

No formal statistical hypothesis testing is planned for this study. This study is designed to collect PK data in Japanese subjects after a single oral administration of Prezcobix under a fed condition.

OVERVIEW OF STUDY DESIGN

This is a single center open-label, single oral dose study in healthy Japanese adult subjects. The study consists of 3 phases; a screening phase from Day -21 to Day -2, an in-patient phase from Day -1 to Day 4 (dosing day is Day 1), and a follow-up assessment phase scheduled 7 to 10 days after the intake of the study drug or at the time of early withdrawal.

SUBJECT POPULATION

Eight subjects will be enrolled to ensure that at least 6 subjects complete the study up to Day 4. If more than 2 subjects withdraw from the study before completion up to Day 4 for reasons other than safety, additional subjects will be enrolled to ensure that at least 6 subjects complete the study up to Day 4.

Main Criteria for Inclusion

Healthy Japanese men and women between 20 and 55 years of age, inclusive; body mass index (BMI) between 18.0 and 30.0 kg/m², inclusive; and body weight not less than 50 kg.

DOSAGE AND ADMINISTRATION

One Prezcobix tablet will be taken in the morning on Day 1. The study drug will be taken orally with 240 mL of noncarbonated water within 30 minutes after start of the standardized breakfast, and the breakfast should be fully ingested within 30 minutes. The study drug must be swallowed whole, not chewed, divided, dissolved or crushed.

PHARMACOKINETIC EVALUATIONS

Venous blood will be collected for the determination of plasma concentrations for each component of DRV/COBI at the following time points;

- Predose, 0.5, 1, 1.5, 2, 2.5, 3, 4, 5, 6, 9, 12, 16, 20, 24, 36, 48, 60, 72 hours postdose and early withdrawal visit

Based on the individual plasma concentration-time data, using the actual sampling times, the following PK parameters will be estimated by noncompartmental analysis. Additional PK parameters may be estimated as well.

PK parameters for DRV and COBI: C_{\max} , C_{last} , t_{\max} , AUC_{last} , AUC_{∞} , λ_z , $t_{1/2,\text{term}}$

SAFETY EVALUATIONS

Safety will be evaluated throughout the study. Following evaluations will be performed according to the TIME AND EVENTS SCHEDULE.

- Adverse Events (AEs)
- Clinical Laboratory Tests
 - - Hematology Panel
 - - Biochemistry Panel
 - - Urinalysis
- 12-lead Electrocardiogram (ECG)
- Vital Signs (blood pressure, pulse, temperature [axillary], respiration rate)
- Physical Examination

Any clinically significant abnormalities persisting at the end of the study will be followed by the investigator until resolution or until reaching a clinically stable endpoint.

STATISTICAL METHODS

Sample Size Determination

Eight subjects will be enrolled in the study to ensure that at least 6 subjects complete the study assessments up to Day 4. Based on a previous study, TMC114FD1003, the maximum observed value of between subject coefficient of variation (CV) for C_{\max} , AUC_{last} and AUC_{∞} for DRV and COBI after intake of DRV/COBI as an FDC tablet under fed conditions were 35% for DRV and 44% for COBI in healthy nonJapanese adult subjects. Using an estimate of approximately 40% for between subject CV and a

sample size of 6 subjects, the true mean C_{\max} , AUC_{last} and AUC_{∞} for each component of DRV/COBI are estimated to be within 73% to 137% of the observed geometric means with 90% confidence.

Pharmacokinetics

All subjects receiving the study drug and having at least one plasma concentration data after administration will be included in the pharmacokinetic analysis. Plasma concentration data will be tabulated for each component of DRV/COBI. Individual and mean concentration time profiles for each analyte will be visually presented on a linear and logarithmic scale. PK parameters for each analyte will be calculated using data of all the subjects whose concentration-time profiles allow for accurate calculation of PK parameters. The descriptive statistics (eg, number of collected data, mean, standard deviation, median, minimum, maximum, CV and geometric means) of plasma concentrations of each analyte at each time point will be reported. Individual and descriptive statistics of PK parameters of each analyte will be tabulated.

Safety

All subjects who received the study drug will be included in the safety and tolerability analysis. Baseline for all laboratory evaluations, vital signs and ECG will be defined as the last evaluation done before the study drug administration. Safety will be evaluated by examining frequency, severity and type of AEs, and changes in clinical laboratory test values (hematology, biochemistry and urinalysis), physical examination results, vital signs and ECG measurements. Safety data will be summarized using descriptive statistics and frequency tables.

TIME AND EVENTS SCHEDULE

Phase	Screening	In-patient period														End-of-Study							
Study day	Days -21 to -2	Day -1	Day 1												Day 2	Day 3	Day 4	End of Study (Day 7 – 10) or Early Withdrawal					
Time			0 h	0.5 h	1 h	1.5 h	2 h	2.5 h	3 h	4 h	5 h	6 h	9 h	12 h	16 h	20 h	24 h	36 h	48 h	60 h	72 h		
Informed consent (ICF)	X																						
Inclusion/exclusion criteria	X																						
Weight/height	X																						
Medical history and demographics	X																						
Smoking habits	X																						
Urine drug/Breath alcohol test	X	X																					
FSH	X ^e																						
Serum pregnancy test ^a	X ^f																					X ^f	
Urine pregnancy test		X ^f																					
Dispense/administer study drug			X																				
Physical examination	X	X	X																		X	X	
Vital signs ^{a,b}	X	X	X										X							X		X	
Serology ^{a,c}	X																						
12-lead ECG ^a	X	X	X										X							X		X	
Clinical Labs ^d	X	X																		X		X	
Blood sample for PK			X	X	X	X	X	X	X	X	X	X	X	X	X	X	X	X	X	X	X	X ^g	
Residence in clinic		<—————>																					
Concomitant medication		throughout the study																					
Adverse events		throughout the study																					

Footnotes:

a. When blood samples are to be collected and 12-lead ECG and/or vital signs are to be checked at the same time point, blood samples will be collected after completion of other evaluations.

- b. Vital signs include respiration rate, supine blood pressure, pulse and temperature (axillary) after more than 5 minutes rest.
- c. Serology tests include HIV antigen/antibody, hepatitis A virus (HAV) antibody immunoglobulin M (IgM), hepatitis B surface antigen (HBsAg), hepatitis C virus (HCV) antibody, and serologic test for syphilis.
- d. Clinical labs include hematology, biochemistry and urinalysis. Subjects will fast for at least 10 hours prior to the blood sampling for clinical labs.
- e. For postmenopausal women only.
- f. For women of childbearing potential only.
- g. For the early withdrawal visit only.

ABBREVIATIONS

AE	Adverse Event
AIDS	Acquired Immune Deficiency Syndrome
ALT	alanine aminotransferase
ARV	antiretroviral
AUC_{last}	area under the plasma concentration-time curve from time zero to time the last quantifiable time, calculated by linear trapezoidal summation
AUC_{∞}	area under the plasma concentration-time curve from time zero to infinite time
BMI	body mass index
C_{last}	concentration at last quantifiable time point
C_{max}	maximum plasma concentration
COBI	cobicistat
CRF	case report form
CV	coefficient of variation
CYP	cytochrome P450
DRV	Darunavir
ECG	electrocardiogram
eDC	electronic data capture
FDC	Fixed-dose combination
FSH	follicle stimulating hormone
GCP	Good Clinical Practice
HAV	hepatitis A virus
HBsAg	hepatitis B surface antigen
HCV	hepatitis C virus
HIV	human immunodeficiency virus
ICF	informed consent form
ICH	International Council for Harmonisation
IEC	Independent Ethics Committee
IgM	immunoglobulin M
IRB	Institutional Review Board
PI	protease inhibitor
PK	pharmacokinetic
PQC	Product Quality Complaint
RBC	red blood cell
rtv	ritonavir
SAE	Serious Adverse Event
$t_{1/2,term}$	terminal elimination half-life
t_{max}	time to reach the maximum plasma concentration
US	United States
WBC	white blood cell
λ_z	elimination rate constant associated with the terminal phase

1. INTRODUCTION

Darunavir (DRV) / cobicistat (COBI) Fixed-Dose Combination Tablet (Prezcobix®) is a fixed dose combination (FDC) tablet containing DRV 800 mg and COBI 150 mg, which enables simplification of the regimen for human immunodeficiency virus (HIV) infection.

For the most comprehensive nonclinical and clinical information regarding Prezcobix, refer to the latest version of the package insert and interview form for Prezcobix

The term "sponsor" used throughout this document refers to the entities listed in the Contact Information page (s), which will be provided as a separate document.

DRV is a protease inhibitor (PI) with potent in vitro activity demonstrated against native human immunodeficiency virus (HIV) and multi-resistant clinical isolates. COBI is an investigational pharmacokinetic enhancer of CYP3A substrates without intrinsic antiretroviral (ARV) activity.

1.1. Background

HIV infection and the Acquired Immune Deficiency Syndrome (AIDS) caused by its infection have serious impacts to human and socio-economics. In 2014, it was estimated that there are 36.9 million HIV patients across the world. In 2014, there were 2.0 million patients with new HIV infection globally and 1.6 million deaths. As of 27 December 2015, 17,909 HIV-infected patients and 8,086 AIDS patients were reported in Japan. In 2015, Japan reported 1,006 new HIV infections and 428 new AIDS cases.² Introduction of combination antiretroviral therapy (ART) has led to a dramatic reduction in mortality and morbidity in treated HIV-infected individuals. Further improvements in therapy and outcome have been challenged by limitations of the commercially available ARV agents, including safety and tolerability, dosing complexity, and the emergence of viral resistance resulting in reduced ARV activity.

DRV

DRV in combination with low dose ritonavir (rtv), as well as other ARV agents, is currently indicated for the treatment of HIV infection in adult patients.

DRV is a HIV protease inhibitor with potent in vitro activity against wild-type HIV-1. As a result of the drug-screening program aimed at activity against resistant strains of HIV-1, DRV is also active against a large panel of viruses resistant to currently licensed protease inhibitor (PI). DRV has been developed in combination with low-dose rtv which serves as a pharmacokinetic enhancer of DRV.

COBI

COBI is an investigational pharmacokinetic enhancer of CYP3A substrates without intrinsic ARV activity. COBI is a potential substitute for rtv and also has the advantage of being able to be coformulated with DRV resulting in a reduced pill burden and potentially fewer adverse effects. This could result in better adherence to the dosing regimen and therefore less risk in the development of resistance.

DRV/COBI Fixed-Dose Combination Tablet (Prezcobix®)

DRV/COBI FDC (Prezcobix®) tablet is a novel combination tablet containing fixed doses of DRV, a PI and COBI which acts as pharmacoenhancer has been developed in a collaboration research by Janssen Research & Development and Gilead Sciences Inc. One tablet of DRV/COBI combination tablet contains these compounds at the respective recommended dose (DRV 800 mg [ethanol additive as 800 mg of darunavir] and COBI 150 mg (150 mg as cobicistat): this combination tablet must be administered in combination with other ARV drugs.

DRV/COBI FDC (Prezcobix®) has been approved in United States (US) and European Union (EU) countries. In Japan, the DRV/COBI FDC has been approved under the trade name of Prezcobix in November 2016.

Clinical Studies

Prezcobix demonstrated its efficacy and tolerability in phase 3 clinical study (Study GS-US-216-0130) conducted outside Japan involving adult anti-HIV drugs-naïve patients with HIV infections or anti-HIV drug-treated patients with HIV infections without mutations associated with resistance to DRV.

1.2. Overall Rationale for the Study

This study is designed to evaluate the Pharmacokinetic (PK) of DRV/COBI after single oral administration of Prezcobix combination tablet to healthy Japanese adult subjects.

In Japan, the applications for approval for anti-infective drugs for HIV which are approved in foreign country can be submitted without clinical data in Japanese subjects, and their quality, safety and efficacy will be evaluated based on foreign data (ref. “Handling of applications for import or manufacturing approval of anti-infective drugs for HIV” [PMSB / ELD Notification No.1015 dated November 12,1998]). In this case, it is allowed to conduct a study to evaluate PK profiles in Japanese subjects after marketing authorization.

According to this notification, after approval of Prezcobix in US, Janssen Pharmaceutical K.K. submitted the new drug application of Prezcobix only with foreign data, and obtained aproval in Japan in November 2016 with the condition that a clinical single-dose PK study in healthy Japanese subjects will be conducted as a postmarketing study.

2. OBJECTIVES AND HYPOTHESIS**2.1. Objectives****2.1.1. Objectives****Primary Objective**

The primary objective is to evaluate the PK of DRV and COBI after a single oral administration of Prezcobix to healthy Japanese adult subjects.

Secondary Objective

The secondary objective is to evaluate the safety after a single oral administration of Prezcobix to healthy Japanese adult subjects.

2.2. Hypothesis

No formal statistical hypothesis testing is planned for this study. This study is designed to collect PK data in Japanese subjects after a single oral administration of Prezcobix under a fed condition.

[figure not shown]
3. STUDY DESIGN AND RATIONALE

3.1. Overview of Study Design

This is a single center open-label, single oral dose study in healthy Japanese adult subjects. Eight subjects will be enrolled to ensure that at least 6 subjects complete the study up to Day 4. The study consists of 3 phases; a screening phase from Day -21 to Day -2, an in-patient period-phase from Day -1 to Day 4 (dosing day is Day 1), and an End of Study phase with a visit scheduled 7 to 10 days after the intake of study drug or at the time of early withdrawal.

As depicted in [Figure 1](#), eight subjects who satisfy all inclusion criteria and do not meet any exclusion criteria will receive Prezcobix at Day 1. Subjects who met the selection criteria at screening will be admitted to the investigational institute on the day before administration (Day -1). All enrolled subjects will receive a single oral dose of one Prezcobix tablet on Day 1 (there is no Day 0) within 30 minutes after start of the standardized breakfast (see [Figure 1](#)), and the breakfast should be fully ingested within 30 minutes. All subjects will remain in the investigational institute for the entire duration of the in-patient phase. Subjects will be discharged on Day 4 after the completion of all required assessments. Subjects will visit the investigational institute on the days as scheduled until the last follow-up assessment on Day 7 - Day 10. Serial blood samples for the determination of plasma concentrations for each component of Prezcobix will be collected over a period of 72 hours. Details on the timing of the dose and the PK and safety assessments are given in the [TIME AND EVENTS SCHEDULE](#).

Figure 1: Schedule Overview of the Study

3.2. Study Design Rationale

This open-label, single-arm, single-dose study design is a commonly used design for required postmarketing studies to evaluate PK of anti-HIV drugs in Japan.

This study is designed to evaluate the pharmacokinetics (PK) of DRV and COBI after single dose administration of Prezcobix to healthy Japanese subjects, since there are currently no PK data after administration of Prezcobix to Japanese subjects.

The dose regimen is a single oral dose of Prezcobix taken under a fed condition is selected since this dose is approved for once daily use in Japan and is how it is currently being used in clinical practice.

The frequent blood samplings especially on Day 1 are set to accurately evaluate the PK profiles of each component with different absorption and elimination rates. A t_{max} and $t_{1/2}$ for DRV and COBI in previous study (TMC114IFD1003 in healthy nonJapanese adult subjects) are summarized in [Table 1](#).

Table 1: PK parameter for DRV and COBI in previous study (TMC114IFD1003)

PK parameter	t_{max} : median (min-max), $t_{1/2,term}$: mean (standard deviation)	
	N=40	
	DRV	COBI
t_{max} (h)	4.03 (1.50 - 9.50)	4.00 (1.00 - 5.02)
$t_{1/2,term}$ (h)	6.7 (3.4)	3.8 (0.8)

The blood sampling points in this study are decided as in TMC114IFD1003 study.

Venous blood will be collected for the determination of plasma concentrations for each component of DRV/COBI at the following time points;

Predose, 0.5, 1, 1.5, 2, 2.5, 3, 4, 5, 6, 9, 12, 16, 20, 24, 36, 48, 60 and 72 hours postdose

4. SUBJECT POPULATION

Screening for eligible subjects will be performed within 21 days before administration of the study drug.

Eight subjects will be enrolled to ensure that at least 6 subjects complete the study up to Day 4. If more than 2 subjects withdraw from the study before completion up to Day 4 for reasons other than safety, additional subjects will be enrolled to ensure that at least 6 subjects complete the study up to Day 4.

The inclusion and exclusion criteria for enrolling subjects in this study are described in the following 2 subsections. If there is a question about the inclusion or exclusion criteria below, the investigator should consult with the appropriate sponsor representative before enrolling a subject in the study.

4.1. Inclusion Criteria

Each potential subject must satisfy all of the following criteria to be enrolled in the study:

1. Subject must be a Japanese man or woman 20 to 55 years of age, inclusive.
2. Subject must be healthy on the basis of physical examination, medical history, vital signs, and 12-lead ECG performed at screening. This determination must be recorded in the subject's source documents and initialed by the investigator.
3. Subject must be healthy on the basis of clinical laboratory tests performed at screening. If the results of the serum chemistry panel, hematology, or urinalysis are outside the normal reference ranges, the subject may be included only if the investigator judges the abnormalities or deviations from normal to be not clinically significant or to be appropriate and reasonable for the population under study with exception of those parameters listed explicitly in the exclusion criteria. This determination must be recorded in the subject's source documents and initialed by the investigator.
4. Each subject must sign an informed consent form (ICF) indicating that he or she understands the purpose of, and procedures required for, the study and are willing to participate in the study.
5. A woman of childbearing potential must have a negative serum (β -human chorionic gonadotropin [β -hCG]) at screening and urine pregnancy test at the time of admission to the study site, hospitalization, and must not breast feed from screening onwards.
6. Contraceptive use by men or women should be consistent with local regulations regarding the use of contraceptive methods for subject participating in clinical studies.

Before study drug administration, a woman must be either:

- a. Not of childbearing potential defined as:
 - premenarchal
A premenarchal state is one in which menarche has not yet occurred.
 - postmenopausal
A postmenopausal state is defined as no menses for 12 months without an alternative medical cause. A high follicle stimulating hormone (FSH) level (>40 IU/L or mIU/mL) in the postmenopausal range may be used to confirm a postmenopausal state in women not using hormonal contraception or hormonal replacement therapy, however in the absence of 12 months of amenorrhea, a single follicle stimulating hormone (FSH) measurement is insufficient.
 - permanently sterile
Permanent sterilization methods include hysterectomy, bilateral salpingectomy, bilateral tubal occlusion/ligation procedures, and bilateral oophorectomy.

b. Of childbearing potential and

practicing a highly effective method of contraception (failure rate of <1% per year when used consistently and correctly)

Examples of highly effective contraceptives include

- user-independent methods:

implantable progestogen-only hormone contraception associated with inhibition of ovulation; intrauterine device (IUD); intrauterine hormone-releasing system (IUS); vasectomized partner; sexual abstinence (*sexual abstinence is considered a highly effective method only if defined as refraining from heterosexual intercourse during the entire period of risk associated with the study drug. The reliability of sexual abstinence needs to be evaluated in relation to the duration of the study and the preferred and usual lifestyle of the subject.*)

- user-dependent methods:

combined (estrogen- and progestogen-containing) hormonal contraception associated with inhibition of ovulation: oral, intravaginal, and transdermal; progestogen-only hormone contraception associated with inhibition of ovulation: oral and injectable

Typical use failure rates may differ from those when used consistently and correctly. Use should be consistent with local regulations regarding the use of contraceptive methods for subjects participating in clinical studies. Hormonal contraception may be susceptible to interaction with the study drug, which may reduce the efficacy of the contraceptive method.

If a woman is of childbearing potential, she must agree to remain on a highly effective method throughout the study and for at least 30 days after the last dose of study drug.

7. A woman must agree not to donate eggs (ova, oocytes) for the purposes of assisted reproduction during the study and for a period of at least 30 days after intake of the study drug.
8. In addition to the user independent highly effective method of contraception, a male or female condom with or without spermicide is required. Male condom and female condom should not be used together (due to risk of failure with friction).
9. During the study and for a minimum of 1 spermatogenesis cycle (defined as approximately 90 days) after receiving the dose of study drug, in addition to the highly effective method of contraception, a man.
 - who is sexually active with a woman of childbearing potential must agree to use a barrier method of contraception (eg, condom with spermicidal foam/gel/film/cream/suppository).
 - who is sexually active with a woman who is pregnant must use a condom must agree not to donate sperm.

10. Subject must be willing and able to adhere to the prohibitions and restrictions specified in this protocol.
11. Body mass index (BMI; weight [kg]/height² [m²]) between 18 and 30 kg/m² (inclusive), and body weight not less than 50 kg.
12. Blood pressure (after the subject is supine for 5 minutes) between 90 and 140 mm Hg systolic, inclusive, and no higher than 90 mm Hg diastolic.
13. Nonsmoker or subject who habitually smokes no more than 10 cigarettes or equivalent of e-cigarettes, or 2 cigars, or 2 pipes of tobacco per day for at least 6 months before study drug administration.
14. Subjects must agree to comply with contraceptive measures as mentioned in Section 4.3 (Prohibitions and Restrictions).

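### Inclusion criteria 6b and 8 do not fit together: the added condom is tied to user-independent methods, although 6b also accepts user-dependent hormonal methods and warns that the study drug may weaken them

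*Protocol*

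**What the plan says.** All of the relevant text is in the Protocol; the SAP has no contraception rule.

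- **Section 4.1, criterion 6b, general requirement.** A woman of childbearing potential must be "practicing a highly effective method of contraception (failure rate of <1% per year when used consistently and correctly", and "she must agree to remain on a highly effective method throughout the study and for at least 30 days after the last dose".
- **Criterion 6b, user-independent examples.** "implantable progestogen-only hormone contraception associated with inhibition of ovulation; intrauterine device (IUD); intrauterine hormone-releasing system (IUS); vasectomized partner; sexual abstinence".
- **Criterion 6b, user-dependent examples.** "combined (estrogen- and progestogen-containing) hormonal contraception associated with inhibition of ovulation: oral, intravaginal, and transdermal" and "progestogen-only hormone contraception associated with inhibition of ovulation: oral and injectable". Every example in this group is hormonal.
- **Criterion 6b, warning.** "Hormonal contraception may be susceptible to interaction with the study drug, which may reduce the efficacy of the contraceptive method".
- **Criterion 8.** "In addition to the user independent highly effective method of contraception, a male or female condom with or without spermicide is required".
- **Criterion 9, male subjects.** A barrier is required "in addition to the highly effective method of contraception, a man" is already relying on, with no restriction to user-independent methods.

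Three other clauses bear on the point. Criterion 14 sends the reader to Section 4.3. Section 4.3, item 2, sends the reader back to the inclusion criteria. Section 8 refers to the methods in Section 4 and adds that women must be willing to keep using them during the study and for at least 30 days after dosing.

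**The concern.** The warning in 6b covers hormonal contraception in general. Among the hormonal methods listed, the implant and the hormone-releasing intrauterine system are user-independent, so criterion 8 gives them a condom. The combined oral, intravaginal and transdermal methods and the progestogen-only oral and injectable methods are user-dependent, and criterion 8 does not mention them. The wording therefore attaches the back-up to some methods with no hormonal component, such as a vasectomized partner, and leaves it off a group that the protocol itself flags as possibly weakened by the drug.

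This is an eligibility and subject-protection rule. Section 4.3 describes the effects of the drugs on conception and fetal development as unknown. A site that reads criterion 8 literally could enrol a woman on the pill without asking for a barrier. A site that reads it strictly could turn away a woman whom 6b admits.

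**Working it through.** **Text check: two readings of criterion 8**

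| Woman's method under 6b | Covered by the interaction warning? | Literal reading of criterion 8 | Cumulative reading (all criteria must be met) |
|---|---|---|---|
| Implant, hormone-releasing system | Yes | Condom added | Eligible with condom |
| Non-hormonal IUD, vasectomized partner | No | Condom added | Eligible with condom |
| Abstinence | No | Condom added, which makes little sense | Same |
| Combined oral, intravaginal, transdermal | Yes | No back-up stated | Not eligible, although 6b accepts the method |
| Progestogen-only oral, injectable | Yes | No back-up stated | Not eligible, although 6b accepts the method |

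The literal reading leaves the last two rows without a stated back-up. The cumulative reading is protective but contradicts 6b. It also sits badly with Section 4.3, item 11, and Section 8, both of which permit birth control drugs.

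**Does another clause decide it?** Criterion 14 leads to Section 4.3, item 2, which leads back to the inclusion criteria. Section 8 leads back to Section 4. None of them names a back-up for user-dependent methods. Section 8 does settle how long the Section 4 methods must be continued.

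**Size of the risk**

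Inputs: the annual failure ceiling of 1% and the 30-day period come from criterion 6b. Eight subjects are planned (Section 3.1), with no sex split, so 0 to 8 women could be concerned (more only if withdrawn subjects are replaced).

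- Per woman over 30 days: 1 − (1 − 0.01)^(30/365) = 0.00083. Because 6b says under 1%, the risk is below 0.083%.
- Any pregnancy, if all eight were such women: 1 − (1 − 0.00083)^8 = 0.0066, so below 0.66%.

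**Duration of exposure**

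Table 1 of Section 3.2 gives mean (SD) terminal half-lives of 6.7 (3.4) h for DRV and 3.8 (0.8) h for COBI.

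- Five half-lives at the mean: 5 × 6.7 = 33.5 h for DRV; 5 × 3.8 = 19 h for COBI.
- At mean + 2 SD: DRV 6.7 + 6.8 = 13.5 h, and 5 × 13.5 = 67.5 h; COBI 3.8 + 1.6 = 5.4 h, and 5 × 5.4 = 27 h.
- Fraction of DRV left at 72 h, 2^(−72/t½): 0.06% at the mean and 2.5% at mean + 2 SD. For COBI it is below 0.01% in both cases.

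All four five-half-life times fall within the 72 hours for which Section 4.3, item 14, keeps subjects at the site.

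**The case against.** The strongest reply is that this is an ambiguity and not a demonstrated error. Because every criterion must be met, criterion 8 can be taken to require a user-independent method plus a condom from all women of childbearing potential, and then nobody goes without a back-up. That is a fair reading, but it turns 6b's user-dependent list into a list of methods that do not qualify, so the text still needs correcting. The documents do not show which meaning was intended.

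Other safeguards also stand. Section 8 asks that package-insert guidance be respected for hormonal contraceptives, and criteria 6 and 6b defer to local regulations. Either may name a back-up, so the point is limited to what the protocol itself states. Exclusion criteria 9 and 14 cover contraindications and the subject's best interest. Section 4 directs eligibility questions to the sponsor before enrolment, though that helps only if the site notices a question. Pregnancy is tested at screening, Day -1 and end of study; the tests detect pregnancy but do not prevent it.

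Two further inferences are tempting. A reader might conclude that criterion 8 leaves the condom without a time limit, since it gives none itself. Section 8 supplies one: the Section 4 methods continue through the study and for at least 30 days after dosing. A reader might also take the broader male rule in criterion 9 as proof of a slip in criterion 8. The contrast is suggestive only: the male rule runs for about 90 days, one spermatogenesis cycle, and Section 12.3.3 gives unknown effects on sperm as a separate concern.

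**Conclusion.** The point holds as a minor wording defect. Criteria 6b and 8 cannot both be applied as they stand without either omitting a back-up for the hormonal methods that 6b warns about or excluding methods that 6b accepts, and no other protocol clause chooses between these.

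The consequence is small: below 0.083% per woman over 30 days, on the assumption that the method performs to 6b's ceiling. A reader might suppose that the interaction raises this risk several-fold over the whole month. The documents give no figure for the size or duration of the interaction. The Table 1 half-lives put most of the exposure inside confinement, provided that they carry over to Japanese subjects and that the interaction fades as the drugs clear. Nor do the documents show that any woman would in fact go without a back-up, because the package insert and local regulations are not available here. No PK objective, sample-size figure or analysis is affected.

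**What to change.** Change the opening condition of criterion 8 so that the condom is added to the highly effective method in use, whether user-independent or user-dependent, other than sexual abstinence. Leave the rest of the criterion as it is. This keeps the condom already asked for with an IUD or a vasectomized partner and extends it to the user-dependent hormonal methods. Section 8 needs no change.

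If the intention was that every woman of childbearing potential should use a user-independent method, delete the user-dependent examples from 6b instead.

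Either change alters an eligibility rule, so it needs a protocol amendment with IEC/IRB approval and any matching consent-form revision (Sections 16.2.2 and 17.1). It adds no visit or test. The downside is a minor burden for women on user-dependent methods or, under the alternative, fewer eligible women.
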